8.3 Dissemination of results

At the end of the study, the principal investigator will submit a report on the study and its main outcome. This report will be shared with the national malaria control programme and the Ministry of Health. The results will seek for the publication in the peer review journal. The meeting with provincial health supervisors and also local community leaders will be conducted after the preliminary results are available after the completion of the study at each study site.

8.4 Amendments to the protocol

After the protocol has been accepted, no change may be made without the agreement of the principal investigator, the sponsor(s) and the institutional review boards.

9. ETHICAL CONSIDERATIONS

9.1 Approval by the national ethical committee

Before study initiation, official approval to conduct the study will be obtained from National Ethics Committee at Institute of Public Health, Cambodia. The study key information will be posted on a public clinical trial registry (<http://www.ANZCTR.org.au>).

9.2 Informed consent

Patients will be included in the study only if they (if adults included) or parents or guardians of children give informed consent. The consent request is available in English and translated into Khmer, will be read entirely to the patient, parent or guardian. Details about the study and its benefits and potential risks will be explained. Once any questions have been answered, a signature will be requested on the document (Appendix 10). If the patient is illiterate, a literate witness must sign; if possible, the signatory will be selected by the prospective participant and will have no connection to the research team. The principal investigator must also obtain and document the assent of children over the age of 12 years and 18 years, but their assent should be accompanied by the consent of a parent or guardian. A child aged between 12 and 18 years who does not agree to participate will not be enrolled in the study and will be referred the health facility staff to be treated according to the standard of care established by the Ministry of Health. Written consent statement for the pregnancy test and the need for contraception is also required for female participants of child-bearing age who are sexually active.

9.3 Confidentiality

All information on patients will remain confidential and be shared only by the study team. Unique identifiers will be used for computer-based data entry and blood samples. In all cases, the principal investigator will ensure that screening forms, the case report form and the completed identification code list are kept in locked files.

9.4 Health-care services

Free health care throughout follow-up for any illness related to malaria will be provided to the study patients regardless of treatment outcome; this includes any expenses related to hospital admission and to adverse medicine reactions, if required.

When prospective or actual participants are found to have diseases unrelated to malaria, the principal investigator should advise them to obtain, or refer them for, medical care.

Any person who decides not to participate or who cannot be enrolled into the study because he or she does not meet the criteria will be referred to the health facility staff. Such people will be treated with antimalarials recommended in the first line treatment in the national treatment guideline and followed-up according to the standard of care established by the Ministry of Health. The principal investigator will ensure that this antimalarial drug is available at the health center.

If a patient is withdrawn from the study before he or she has completed the full course of the treatment, the physician must make all necessary arrangements to provide the patient with the full dose of the medicine being tested or with a full course of antimalarials—ASMQ or ASP (Annex 3) based on the areas where the study site is—recommended in the national treatment guideline.

9.5 Reimbursement and compensation

Subjects shall be reimbursed for their transport to attend all visits to the health center. Insecticide treated nets will be provided to participants. No other gifts or payments will be made.

9.6 Community

Even though the study is health facility-based the community will be informed about the presence of and study purposes. The researchers will meet with the provincial health departments and ask for the collaboration and coordination between the researchers and VMWs/VHVs in the catchment areas of HCs under the study. The researcher will send one of research team members to attend the VMWs/VHVs monthly meeting to inform the community about the progress study and seek for further collaboration from the community.

9.7 Clinical trial registration

As required by WHO, it is necessary to register all therapeutic efficacy studies being done by the country. The clinical trial registration will be done by the Ministry of Health through NMPE on these recommended websites: <http://www.ANZCTR.org.au> or www.clinicaltrials.gov

[figure not shown]

Figure 1: Study sites for 2020

Appendix 1. Definition of severe falciparum malaria⁶

Severe manifestation of *P. falciparum* malaria in adults and children

Clinical manifestations

- prostration,
- impaired consciousness,
- respiratory distress (metabolic acidosis),
- multiple convulsions,
- circulatory collapse,
- pulmonary oedema (radiological),
- abnormal bleeding,
- jaundice,
- haemoglobinuria.

Laboratory findings

- severe anaemia (haemoglobin < 5 g/dl, haematocrit < 15%),
- hypoglycaemia (blood glucose < 2.2 mmol/l or 40 mg/dl),
- acidosis (plasma bicarbonate < 15 mmol/l),
- hyperlactataemia (venous lactic acid > 5 mmol/l),
- hyperparasitaemia (> 4% in non-immune patients),
- renal impairment (serum creatinine above normal range for age).

Classification of severe malaria in children

Group 1: children at increased risk for death

- prostration
- respiratory distress

Group 2: children at risk for clinical deterioration

- haemoglobin < 5 g/dl, haematocrit < 15%
- two or more convulsions within 24 h

Group 3: children with persistent vomiting

⁶ World Health Organization. Severe falciparum malaria. *Transactions of the Royal Society of Tropical Medicine and Hygiene*, 2000, 94(Suppl. 1):1–90.

APPENDIX 2. MEDICATIONS (WITH ANTIMALARIAL ACTIVITY) THAT SHOULD NOT BE USED DURING THE STUDY PERIOD

- chloroquine, amodiaquine;
- quinine, quinidine;
- mefloquine, halofantrine, lumefantrine;
- artemisinin and its derivatives (artemether, arteether, artesunate, dihydroartemisinin);
- proguanil, chlorproguanil, pyrimethamine;
- sulfadoxine, sulfalene, sulfamethoxazole, dapsons;
- primaquine;
- atovaquone;
- antibiotics: tetracycline*, doxycycline, erythromycin, azythromycin, clindamycin, rifampicin, trimethoprim;
- pentamidine.

* Tetracycline eye ointments can be used.

APPENDIX 3. DOSING CHART OF SURVEILLANCE ACT

ASMQ (Artesunate + Mefloquine co formulated)

The adult dose tablet contains 100mg Artesunate plus 200mg Mefloquine.

Weight (kg)	D0	D1	D2
18-29	1p	1p	1p
≥30	2p	2p	2p

Pyronaridine-artesunate (Pyramax®, Shin Poong Pharmaceuticals). One tablet contains 60mg artesunate+ 180mg pyronaridine. Dosing will be according to body weight.

Table 1: Pyronaridine-artesunate dosage by body weight

Body Weight(kg)	Daily dose(mg)		Number of tablets
	PYR	AS	
20–<24 kg	180	60	1 tab
24–<45 kg	360	120	2 tabs
45–<65 kg	540	180	3 tabs
65 and above	720	240	4 tabs

Pyronaridine-artesunate will be taken orally with water, once daily for 3 days. Each dose will be administered under supervision in the clinic or if not possible by a home visitor to the patient's home. A dose will be repeated in full if vomiting occurs within 30 minutes of

administration of the first day of administration only. This event will be documented in the case record form (CRF).

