3.8 Patient discontinuation or protocol violation

Study patients who meet any of the following criteria will be classified as withdrawn.

- withdrawal of consent. A patient may withdraw consent at any time, without prejudice for further follow-up or treatment at the study site.
- failure to complete treatment, due to:
 - persistent vomiting of the treatment. A patient who vomits the study medication twice will be withdrawn from the study and given rescue treatment.
 - failure to attend the scheduled visits during the first 3 days; or
 - serious adverse events necessitating termination of treatment before the full course is completed. A patient can be discontinued from the study if the principal investigator decides so due to an adverse event of adequate nature or intensity. In this case, information on the adverse event and symptomatic treatment given must be recorded on a case report form. If the adverse event is serious, the principal investigator must notify the sponsor or its designee immediately and follow the reporting procedures described in section 5.3.
- enrolment violation:
 - severe malaria on day 0; or
 - erroneous inclusion of a patient who does not meet the inclusion criteria.
- voluntary protocol violation: self- or third-party administration of antimalarial drug (or antibiotics with antimalarial activity) (Appendix 2);
- involuntary protocol violation:
 - occurrence during follow-up of concomitant disease that would interfere with a clear classification of the treatment outcome;
 - detection of mono-infection with another malaria species during follow-up; or
 - misclassification of a patient due to a laboratory error (parasitaemia), leading to administration of rescue treatment.

Patients who are withdrawn will nevertheless be followed up until recovery or the end of follow-up, if possible; however, no treatment outcome will be assigned to these patients, and they will be censored or excluded from the analysis. The reasons for discontinuation or protocol violation will be recorded on the case report form.

Pregnancy detected during the course of follow-up does not constitute a reason for withdrawal but the event must be recorded and managed as described in section 5.3.

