4. TREATMENT

4.1 Antimalarial treatment

ASMQ (Artesunate + Mefloquine co formulated).

The adult dose tablet contains 100mg Artesunate plus 220mg Mefloquine and the paediatric tablet contain 55mg Artesunate plus 55 mg Mefloquine. (Refer to Annex table for more detailed dosage).

ASP (Artesunate + Pyronaridine/ Pyramax): Adults and children \geq 20 kg (Refer to Annex table for more detailed dosage).

All doses of medicine will be administered under the supervision of a qualified member of the staff designated by the principal investigator. The study patients will be observed for 30 min after medicine administration for adverse reactions or vomiting. Any patient who vomits during this observation period will be re-treated with the same dose of medicine and observed for an additional 30 min. If the patient vomits again, he or she will be withdrawn and offered rescue therapy. The patients are recommended to stay at the health facility until they complete the treatment course for malaria infection.

All doses of medicine will be administered under the supervision of a qualified member of the staff designated by the principal investigator. The study patients will be observed for 30 min after medicine administration for adverse reactions or vomiting. Any patient who vomits during this observation period will be re-treated with the same dose of medicine and observed for an additional 30 min. If the patient vomits again, he or she will be withdrawn and offered rescue therapy. The patients are recommended to stay at the health facility until they complete the treatment course for malaria infection.

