4.3 Rescue treatment

If the patient vomits twice the treatment he/she will receive parenteral therapy based on national treatment guideline. If a patient is unable to tolerate the trial medication he/she should discontinue the treatment and alternative anti-malaria medication should be initiated. In this case, the reason for discontinuation should be recorded in the case record form (CRF) as "Adverse experience" and be withdrawn from the study.

Any patient with sign of severe malaria, will be hospitalized and receive parenteral therapy with artemether or quinine 7 days (IV) + tetracycline 7 days as well as relevant supportive treatments. If a patient meets one of the criteria for therapeutic failure, he/she will receive artemether at D1 3.2mg/kg (max 160mg) intramuscularly, D2 1.6 mg/kg (max 80mg) IM, from D3 to D5 1.6 mg/kg (max 80mg) per day IM and D6 plus mefloquine 25mg/kg spreading over 3 days (max 1250mg) according to the current national recommendations.

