6.2 Follow-up

Patients who meet all the enrolment criteria will be given a personal identification number and will receive treatment only after the study has been fully explained to them and they have willingly provided informed consent. Any person who decides not to participate in the study will be examined, treated and followed-up by the health facility staff according to the standard of care established by the Ministry of Health.

The basic follow-up schedule is summarized in Appendix 6. A case report form (Appendix 7) and a serious adverse event report form (Appendix 8) will be used to record the general information and clinical observations on each patient enrolled into the study. The appointment schedule will be clearly explained, and a follow-up card with a personal identification number will be provided. House visits will be made in the event patient cannot make it to the clinic. If this is the case provide detail about the visiting staff and the study procedures that will be done at home. The health staff will send to the patient's residence and provides a transportation support for bringing the patient to the study site where he or she will receive the physical examination and laboratory test if necessary.

The day a patient is enrolled and receives the first dose of medicine is designated 'day 0'. All antimalarial treatment will be given by a study team member under supervision. Enrolled patients will be observed for at least 30 min after treatment to ensure that they do not vomit the medicine. If vomiting occurs within 30 min of treatment, the full treatment dose will be repeated. Ancillary treatment, such as antipyretics, will be provided if necessary to patients by the study team and documented on the case report form. Patients with persistent vomiting (i.e. necessitating more than a single repeat dose) will be excluded from the study and immediately referred to the health facility staff for appropriate management.

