Thereafter, patients are required to undergo regular clinical reassessment. Blood films for parasite counts will be made on days 2, 3 and 7 and then weekly for the remainder of the follow-up period, i.e. on days 14, 21, 28, 35 and 42. Patients will be advised to return on any day during the follow-up period if symptoms return and not to wait for the next scheduled visit day. In particular, parents or guardians should be instructed to bring children to the centre at any time if they show any sign of danger (unable to drink or breastfeed, vomiting everything, presenting with convulsions, lethargic or unconscious, unable to sit or stand, presenting with difficult breathing), if they are still sick or if there is any cause for worry. Clinical reassessment will be sufficiently thorough to ensure patient safety and will include assessment not only for potential treatment failure but also for potential adverse reactions to the medicine. Additionally, blood films will be obtained whenever parasitological reassessment is requested by the clinical staff.

Because many medicines have to be given over several days, the initial visits are critical not only for assessing efficacy but also for ensuring patient safety; defaulters at this stage will not have received a complete course of treatment and may be at risk for clinical deterioration. All reasonable efforts will be made to find defaulters to ensure complete treatment. Similarly, the ultimate success of the study rests on minimizing loss to follow-up. While patients are encouraged to return on their own for scheduled follow-up visits, it is essential that provisions be made ahead of time for locating patients at home if they do not attend as requested. This requires obtaining detailed directions to the home during enrolment, and study team members familiar with the community will be responsible for home visits and means of transport for the patients. The schedule of treatment and follow-up examinations given in this protocol must be followed to ensure data integrity. Patients who fail to return on days 1 and 2 and miss one dose of the treatment will be withdrawn from the study definitively. After day 3, patients who fail to return on day 7 but are present on day 6 or 8 (likewise days 13/15, days 20/22, days 27/29, days 34/36 and days 41/43) may still be included in the analysis. Deviation from the protocol of more than 1 day should, however, be avoided (see also section 3.7).

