8.2 Analysis of data

Standard WHO spreadsheet will be used for data management and analysis. Data will be analysed by two methods: the Kaplan-Meier method and per-protocol analysis. In addition to the reasons for withdrawal listed in section 3.8, patients will be considered withdrawn from the analysis if the PCR results are unclassifiable or if the results of PCR indicate that the failure is due to reinfection with *P. falciparum*.

The final analysis will include:

- a description of all patients screened and the distribution of reasons for non-inclusion in the study;
- a description of all the patients included in the study;
- the proportion of adverse events and serious adverse events in all the patients included in the study;
- the proportion of patients lost to follow-up or withdrawn, with 95% confidence intervals and a list of reasons for withdrawal;
- the cumulative incidence of success and failure rates at day 28 and 42, PCR-uncorrected and PCR-corrected; and
- the proportion of early treatment failure, late clinical failure, late parasitological failure and adequate clinical and parasitological response at day 28 and 42, with 95%

⁵ WHO/GMP. *Standardized data entry for therapeutic efficacy tests*. Geneva, World Health Organization (<http://www.who.int/malaria/resistance>).

confidence intervals, PCR-uncorrected and PCR-corrected.

Guidelines on calculating the cumulative success or failure rate, the proportion of adequate clinical and parasitological response and treatment failure are given in Appendix 9.

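### Appendix 3 limits the repeat of a vomited ASP dose to the first day, against sections 4.1 and 6.2, and no express rule covers a patient left one dose short

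*Protocol*

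**What the plan says.** Section 4.1 places every dose of both regimens under supervision with 30 minutes of observation, and then states: "Any patient who vomits during this observation period will be re-treated with the same dose of medicine". A second vomit leads to withdrawal and rescue. Section 6.2 agrees: "If vomiting occurs within 30 min of treatment, the full treatment dose will be repeated". Neither section limits the rule to a day or exempts ASP.

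Appendix 3, below the ASP dosing table, gives ASP once daily for 3 days. It repeats a dose in full if vomiting occurs within 30 minutes of "administration of the first day of administration only".

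The rules on what follows vomiting or a lost dose are:
- Section 3.8: "A patient who vomits the study medication twice will be withdrawn from the study and given rescue treatment".
- Section 4.3, first rule: "If the patient vomits twice the treatment he/she will receive parenteral therapy based on national treatment guideline". A second rule stops treatment, starts an alternative antimalarial and withdraws any patient who cannot tolerate the study drug.
- Section 3.8 also lets the principal investigator discontinue a patient for an adverse event of sufficient nature or intensity.
- Section 6.2, on missed visits: "Patients who fail to return on days 1 and 2 and miss one dose of the treatment will be withdrawn from the study definitively".
- Section 9.4 requires a full course to be supplied under this condition: "If a patient is withdrawn from the study before he or she has completed the full course of the treatment".

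On primaquine, the synopsis says that a single dose will be given (0.25 mg base/kg, adult dose 15 mg). The general objective in section 2 gives the same dose without the drug name. Sections 4.1 to 4.3 and the Appendix 6 schedule do not mention it. Appendix 2 lists it among drugs to be avoided during the study.

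**The concern.** The protocol gives two answers to one bedside question: what to do when an ASP patient vomits the second or third dose. This is first a matter of patient safety, because one answer completes the course and the other may leave the patient short of a dose during active infection.

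It also bears on the estimate. The study is meant to tell the Ministry of Health how well ASP works when the full course is taken under observation. If patients who lost a dose stay in the analysis, some failures could reflect incomplete dosing. Any such effect would raise the apparent ASP failure rate, and sites could differ according to which text their staff followed.

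The primaquine gap is similar but smaller: a treatment is promised in the synopsis, and the sections that staff work from say nothing about it.

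**Working it through.** The protocol has no figure of its own for vomiting or partial dosing, so the check is mainly a comparison of texts.

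**Step 1: the conflict by dose.** ASP doses fall on days 0, 1 and 2 (Appendix 6). For one vomit within 30 minutes:

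| Dose vomited | Sections 4.1 and 6.2 | Appendix 3 (ASP) |
|---|---|---|
| 1 (day 0) | repeat | repeat |
| 2 (day 1) | repeat | no repeat |
| 3 (day 2) | repeat | no repeat |

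The texts disagree for two of the three doses.

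**Step 2: follow one patient under Appendix 3.** The patient's only vomit is dose 2 or 3.
1. The dose is not repeated.
2. The vomiting rule in 3.8 and the first rule in 4.3 both need two vomits, so neither applies. Section 3.8 lists specific causes of an incomplete course, and a single vomit is not one of them.
3. The intolerance clause in 4.3 and the adverse-event clause in 3.8 could apply, but no text ties either to a single vomited dose. They depend on judgement.
4. If neither is used, the patient is not withdrawn and the full-course duty in 9.4 does not arise.
5. Section 8.2 defines further withdrawals from the analysis thus: "In addition to the reasons for withdrawal listed in section 3.8", adding only unclassifiable PCR results and falciparum reinfection. The patient stays in.
6. In the PCR-corrected results, the analysis guideline table counts a falciparum recrudescence as failure and censors or excludes a reinfection. Section 3.1 restricts PCR correction to P. falciparum, so a P. vivax recurrence counts as failure without correction.

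By contrast, the missed-visit rule in 6.2 withdraws a patient who loses one dose by not returning. The same shortfall is handled in two ways.

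**Step 3: what the protocol fixes about size.**
- Patients to whom the clause could apply: 2 ASP sites x 120 = 240, in four site-by-species cohorts of 60. This is a denominator; only those who vomit dose 2 or 3 are affected.
- Course in the 45 to <65 kg band (Appendix 3): artesunate 3 x 180 = 540 mg and pyronaridine 3 x 540 = 1,620 mg. Two doses give 360 mg and 1,080 mg.
- Share kept: 2/3 = 67%, the same in every weight band. This is a floor, because part of a vomited dose may be absorbed and a second vomit leads to withdrawal under 3.8.

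**Step 4: what it does not fix.** No vomiting rate is given. As an assumption only, let a share v of patients vomit at each of doses 2 and 3, independently, and set dose 1 aside. The expected number per cohort who vomit exactly one of them is 60 x 2v(1 - v):
- v = 1%: 60 x 2 x 0.01 x 0.99 = 1.2
- v = 5%: 60 x 2 x 0.05 x 0.95 = 5.7

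These are patients affected, not failures. Turning them into failures needs a failure rate after two doses, which the protocol does not give.

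**The case against.** The strongest reply is that the body of the protocol governs. Section 4.1 prints its rule twice, 6.2 repeats it, and 4.1 sends the reader to the annex only for dosage detail. The outlier is one awkward sentence under a dosing table, and nothing shows that staff would prefer it. That fairly limits the likely reach. It does not remove the conflict: no text says which rule prevails, and Appendix 3 is the ASP-specific text.

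The limit may also be deliberate for ASP. If so, 4.1 and 6.2 are wrong for ASP, and the missing consequence for the unrepeated dose becomes the main issue.

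Two stronger readings are tempting and do not stand. A reader might infer that a patient with one vomit has no route to rescue at all. The intolerance clause in 4.3 has no two-vomit threshold, and 3.8 gives the principal investigator discretion, so a route exists; what is lacking is an express requirement. A reader might also infer that every recurrence in such a patient counts against ASP. In the PCR-corrected results a falciparum reinfection does not.

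**Conclusion.** The contradiction is real and is wrong as written. Under Appendix 3, a patient whose only vomit is ASP dose 2 or 3 may complete as little as two thirds of the course, and withdrawal or completion is left to judgement. The conclusion about the analysis rests on two assumptions: that staff follow Appendix 3, and that the discretionary clauses are not used. Any resulting bias is towards a higher ASP failure rate, but its size cannot be computed from the protocol.

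A reader might try to gauge importance by counting how many extra failures among the 54 required patients would exceed the 8% precision in section 8.1. That figure is a confidence-interval half-width, not a threshold for bias, so the comparison shows nothing here.

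The primaquine gap is secondary: the drug and dose are in the synopsis, but no day of dosing is given and section 4 and the schedule omit it. A reader might infer that Appendix 2 with 3.8 would force withdrawal of patients given protocol primaquine. The documents do not support this. Appendix 2 also lists artesunate and mefloquine, which are study drugs, so it reads as aimed at non-study use, and the 3.8 violation concerns drugs taken by the patient or given by a third party.

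**What to change.** **Vomited doses.** In the Appendix 3 phrase "administration of the first day of administration only", keep the first word and delete the rest, so that the rule in 4.1 and 6.2 covers all three ASP doses.

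If the sponsor confirms that the limit is intended, state the ASP exception in 4.1 and 6.2, and add to 3.8 that a patient with an unrepeated vomited dose is withdrawn. Section 9.4 then supplies a full course. These withdrawals would draw on the allowance in 8.1, which is 60 - 54 = 6 patients per cohort.

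**Primaquine.** Name it in the section 2 objective. Add it to 4.1 and Appendix 6 with its day and dose of 0.25 mg base/kg (adult dose 15 mg). For clarity, except study treatment from the Appendix 2 list. If it is not to be given, remove it from the synopsis and the objective.

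**Cost.** This is a small wording amendment with no change to sample size or visits. Under section 8.4 it needs the agreement of the principal investigator, the sponsor and the review boards. The first option is the cheaper one, because it adds no withdrawal reason.

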1- ASMQ: Trapeang Cho, Kampong Speu district, Kampong Speu province; Chambak, Phnom Srouch district, Kampong Speu; Keo Seima, Saen Monourom, Mondulkiri.

2- ASP: Veunsai, Veunsai district, Rattanakiri; Cheu Tom, Krakor district, Pursat

Study Design: This surveillance study is a one arm prospective study

Patient population by treatment regimen:

Artesunate-Mefloquine (ASMQ)

Febrile patients aged between 18 years and 60 years, with confirmed uncomplicated *P. falciparum* and *P. vivax* infections.

Artesunate-Pyronaridine (ASP)

Febrile patients aged between 2 years and 60 years, with confirmed uncomplicated *P. falciparum* and *P. vivax* infections.

Sample Size: 600 (120 in one site: 60 *P. falciparum* cases and 60 patients *P. vivax* cases)

Treatment(s) and follow-up: artesunate-mefloquine (ASMQ) will follow a dosing chart in Annex 3; one tablet of Pyronaridine-Artesunate contains 60mg artesunate+ 180mg pyronaridine; dosing is given based on the weight band (Annex 3). Primaquine will be administered as a single 15-mg adult dose (0.25 mg base/kg).

Clinical and parasitological parameters will be monitored over a 42-day follow-up period to evaluate drug efficacy.

Primary endpoints: The proportion of patients with early treatment failure, late clinical failure, late parasitological failure or an adequate clinical and parasitological response as indicators of efficacy. Recrudescence will be distinguished from re-infection by polymerase chain reaction (PCR) analysis.

Secondary endpoints: The frequency and nature of adverse events

Exploratory endpoints:

- to assess the in vitro susceptibility of *P. falciparum* isolates to dihydroartemisinin, piperaquine, artesunate and mefloquine at D0 and Day of recrudescence;
- to determine the polymorphism of molecular markers of *Plasmodium falciparum* and Kelch gene

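### Appendix 3 limits the repeat of a vomited ASP dose to the first day, against sections 4.1 and 6.2; if followed, a patient one dose short would still be counted for efficacy

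*Protocol*

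**What the plan says.** Three places in the protocol say what to do when a dose is vomited.

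- **Section 4.1**, covering all supervised doses of both drugs: "Any patient who vomits during this observation period will be re-treated with the same dose of medicine". The period is 30 minutes and no day is singled out.
- **Section 6.2**: "If vomiting occurs within 30 min of treatment, the full treatment dose will be repeated". Again there is no day limit.
- **Appendix 3**, in the text below the ASP dosing table: a dose is repeated in full if vomiting occurs within 30 minutes of "administration of the first day of administration only".

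Two sections say when incomplete treatment leads to withdrawal.

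- **Section 3.8** lists three causes of failure to complete treatment: persistent vomiting ("A patient who vomits the study medication twice will be withdrawn from the study and given rescue treatment"), missed visits in the first three days, and a serious adverse event that ends treatment early.
- **Section 6.2** adds: "Patients who fail to return on days 1 and 2 and miss one dose of the treatment will be withdrawn from the study definitively". It also excludes patients whose vomiting calls for more than one repeat dose.

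Section 8.2 takes the 3.8 reasons as analysis exclusions and adds only PCR-based ones.

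**The concern.** For a single vomit on day 1 or 2 at an ASP site, 4.1 and 6.2 say re-dose and Appendix 3 says do not. The protocol has no order of precedence between body and appendix.

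Two things are at stake. The first is care: a patient treated by the Appendix 3 rule may absorb only two of three daily doses. The second is the estimate: that patient's outcome is still classified, so a failure caused by lost drug would count as a failure of ASP, the drug being re-evaluated to inform treatment policy. A dose lost by absence leads to withdrawal and a dose lost by vomiting does not, although the course is incomplete in both cases.

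**Working it through.** **Step 1. Which doses are affected.** Section 6.2 calls the day of the first dose day 0, and ASP is given once daily for three days, so doses fall on days 0, 1 and 2. The repeat rules compare as follows:

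| Vomit within 30 min on | 4.1 and 6.2 | Appendix 3 (ASP) |
|---|---|---|
| day 0 | repeat | repeat |
| day 1 | repeat | no repeat |
| day 2 | repeat | no repeat |

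The ASMQ part of Appendix 3 has no vomiting rule, so the conflict concerns ASP only.

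**Step 2. How much drug is lost.** At most one of three equal doses. In the 45 to <65 kg band of Appendix 3, that is 540 of 3 × 540 = 1,620 mg pyronaridine and 180 of 3 × 180 = 540 mg artesunate, or one third of each.

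**Step 3. Whether the patient leaves the analysis.** Take an ASP patient who attends every visit, vomits once within 30 minutes on day 1 or 2, and is not re-dosed.

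- 3.8, vomiting twice: not met.
- 3.8, non-attendance: not met.
- 3.8, serious adverse event: not met.
- 6.2, failure to return with a missed dose: not met, because the patient returned.
- 6.2, more than one repeat dose: not met, because none was given.
- 8.2, PCR unclassifiable or reinfection: unrelated to the lost dose.
- The tables in the guidelines for analysis of results: no row for a lost dose.

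The patient is therefore classified and counted. The day 1 and day 2 case report forms record vomiting and its time, so such patients could be identified, but no rule in the protocol uses the entry.

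**Step 4. The plan's own figure.** Section 8.1 uses a failure rate of 10%, 95% confidence and 8% precision:

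n = 1.96² × 0.10 × 0.90 / 0.08² = 54.0, which matches the stated 54. Adding 10% gives 54 × 1.1 = 59.4, rounded up to the stated 60.

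Two ASP sites × two species gives four strata of 60, or 240 planned patients, with 54 evaluable per stratum.

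**Step 5. What one extra failure does.** 1/54 = 1.85 percentage points. The planned half-width is 1.96 × √(0.10 × 0.90 / 54) = 8.0 points, so one failure is 1.85/8.0 = 23% of it. For example, 5/54 = 9.3% becomes 6/54 = 11.1%. This arithmetic holds for any single changed outcome and does not show how often this rule would change one.

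**Step 6. Range under assumptions.** The protocol gives neither a vomiting rate nor a failure rate after two doses. Let v be the share of evaluable patients left a dose short and e their excess failure probability; the stratum failure rate shifts by v × e.

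- Assume 2–5% vomit one dose, spread evenly over three days. Then v = 2/3 of that, or 1.33–3.33%, which is 0.72–1.80 of 54 patients. With e assumed at 10–50%, the shift runs from 0.10 × 1.33 = 0.13 points to 0.50 × 3.33 = 1.67 points.
- Assume more widely that v = 1–10% and that these patients fail at 20–50% instead of 10%, so e = 10–40%. The shift runs from 0.1 to 4.0 points, and the failure rate from 10.1% to 14.0%.

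Both ranges assume that Appendix 3 is always followed. They shrink if vomiting clusters on day 0 or if staff follow 4.1 and 6.2.

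**The case against.** The strongest reply is that under-dosing is conditional. Section 4.1 states its rule twice and covers all doses, and 6.2 repeats it. Staff who work from the body of the protocol will re-dose, and no patient is left short. That stands: the documents show a conflict of instructions, not that patients will in fact be under-dosed.

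A reader might infer that the protocol directs staff to Appendix 3 on this point, since the synopsis says "dosing is given based on the weight band (Annex 3") and 4.1 says "Refer to Annex table for more detailed dosage". Both references concern the number of tablets by weight. Neither hands over the handling of vomiting, which 4.1 sets out itself, so they are weak grounds for expecting the appendix sentence to prevail.

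The sentence in Appendix 3 is also awkwardly worded and may be a drafting slip. That bears on how it arose. As it stands it still carries a limit that contradicts the body.

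Part of the scenario is already covered. A patient who vomits on both day 1 and day 2 can be withdrawn for vomiting twice, and one who cannot tolerate the drug is withdrawn under 4.3. What remains is exactly one vomit, within 30 minutes, on day 1 or 2.

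Rules for incomplete dosing could also sit in a statistical analysis plan that is not at hand. Such a plan could exclude the patient, but it cannot restore a dose that was not given.

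Finally, a reader might see a related clash between 9.4, which offers withdrawn patients the tested drug or ASMQ/ASP, and the rescue treatment in 4.3. The documents do not support making a point of it. Section 4.3 is the specific rule and 9.4 a general duty of care. Severe malaria with parasitaemia on days 1 to 3 is early treatment failure under Appendix 4, not a withdrawal.

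**Conclusion.** The contradiction between Appendix 3 and sections 4.1 and 6.2 is explicit and should be corrected. The consequence for the analysis is conditional: it arises only where staff follow Appendix 3, and then for an ASP patient with a single early vomit on day 1 or 2.

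A reader might infer a material bias against ASP. The documents do not support that. The direction would be towards a higher ASP failure rate, but the size rests entirely on assumed rates and is probably small against the planned 8-point precision. The sample size is unaffected. The case for the change rests mainly on treating the patient fully and dosing the same way at both ASP sites.

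**What to change.** In Appendix 3, keep the first word of "administration of the first day of administration only" and delete the rest, so that the sentence ends at the 30-minute condition and the rule in 4.1 and 6.2 covers every ASP dose.

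If the sponsor does intend a first-day limit for ASP, state it in 4.1 and 6.2, and add *a vomited dose that was not repeated* to the failure-to-complete-treatment criteria in 3.8. A dose lost by vomiting is then handled like a dose lost by absence.

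The cost is a change of wording and, under the first option, an occasional repeat ASP dose on day 1 or 2. The case report forms need no change, since they already record vomiting on those days.
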